12.5 Analysis of Secondary Endpoints

Characterize adverse effects (AE) of nivolumab in combination with ramucirumab in subjects with previously-treated mesothelioma.

Proportion of subjects with each grade of adverse events as defined by CTCAE v4 will be computed along with 95% confidence intervals, and reported in a tabular and descriptive manner.

Median progression free survival (PFS) and overall survival (OS) times will be computed, and PFS rates at 3, 6, and 12 months and OS rates at 2 years +/- 2 months will be calculated with associated 95% confidence intervals. Kaplan-Meier curves for each survival rate will be plotted.

12.6 Analysis of Correlative Endpoints

- PD-L1 expression in tumor tissue (categorical based on 5% threshold) from before therapy (assessed within 14 days before treatment) will be correlated with the best clinical response (modified version of RECIST 1.1) and treatment outcome. Chi-square statistics will be computed.
- Change in PD-L1 expression in tumor tissue from before therapy (assessed within 14 days before treatment) to after 4 cycles (8 weeks) of therapy will be correlated with the best clinical response (modified version of RECIST 1.1) and treatment outcome. Chi-square statistics will be computed.
- Change in cytokine expression in tumor tissue from before therapy (assessed within 14 days before treatment) to after 4 cycles (8 weeks) of therapy will be correlated with the best clinical response (modified version of RECIST 1.1) and treatment outcome. Chi-square statistics will be computed.
- Change in soluble PD-L1 level during therapy (assessed pre-dose Cycles 1 and 5 [(Days 1 and 57 of treatment period, respectively)]) relative to baseline will be examined in relation to the best clinical response (modified version of RECIST 1.1) and treatment outcome. Correlation-statistics will be computed.
- Change in number of CD8+ cells (rich vs. poor) and Granzyme B+ T cells (rich vs. poor) from before therapy (assessed within 14 days before treatment) to after 4 cycles (8 weeks) of therapy will be examined in relation to the best clinical response (modified version of RECIST 1.1) and treatment outcome. Chi-square statistics will be computed.

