2.1.3. Correlative Objectives

- Correlate PD-L1 expression in tumor tissue (from biopsy before treatment) with best clinical response (modified RECIST 1.1 criteria) in subjects with previously-treated mesothelioma.
- Correlate change in PD-L1 expression in tumor tissue from before therapy (assessed within 14 days before treatment) to after 4 cycles (8 weeks) of therapy with best clinical response (modified RECIST 1.1 criteria) at the end of Cycle 4 (Week 8) in subjects with previously-treated mesothelioma.
- Correlate cytokine genes expressions in tumor tissue (such as IL-1, IL-2, IL-6, GM-CSF, IL-10, IL-12, T-bet, IRF1, IFN γ , CXCL1, CXCL9, CXCL10, CCL2 and 5) from before therapy (assessed within 14 days before treatment) to after 4 cycles (8 weeks) of therapy with best clinical response (modified RECIST 1.1 criteria) at the end of Cycle 4 (Week 8) in subjects with previously-treated mesothelioma.

- Correlate change in soluble PD-L1 level in plasma during therapy (assessed pre-dose Cycles 1 and 5 [(Days 1 and 57 of treatment period, respectively)]) relative to baseline with best clinical response (modified RECIST 1.1 criteria) at the end of Cycle 4 (Week 8) in subjects with previously-treated mesothelioma.
- Correlate change in number of CD8+, Granzyme B+ T cells in tumor tissue from before and during therapy (assessed within 14 days before treatment) to after 4 cycles (8 weeks) of therapy with best clinical response (modified RECIST 1.1 criteria) at the end of Cycle 4 (Week 8) in subjects with previously-treated mesothelioma.

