Expression and localization (central versus peripheral) of cytokines in tumor tissue obtained by CT-guided biopsies (i.e., image-guided percutaneous lung biopsy) will be determined by nanostring or comparable technology. Biopsy to include FFPE and snap frozen tissue. Refer to the CLM for collection, labeling and shipping instructions.

9.4 Correlate change in soluble PD-L1 level in serum during therapy (assessed pre-dose Cycles 1 and 5), to the best clinical response (modified RECIST 1.1 criteria) at the end of Cycle 4 (Week 8) in subjects with previously-treated mesothelioma. (mandatory)

Whole blood for serum submission will be collected predose on Cycle 1 Day 1 and Cycle 5 Day 1 for analysis of soluble PD-L1 levels. Change in soluble PD-L1 levels as a result of treatment will be examined in relation to the best clinical response (modified RECIST 1.1 criteria [35]) at the end of Week 4 (Cycle 8). This analysis determined by ELISA assay or comparable technology will be conducted by a lab such as Martell Diagnostic Laboratory, at Roseville, MN. Refer to the CLM for collection, processing, labeling and shipping instructions.

9.5 Correlate change in number of CD8+ cells and Granzyme B+ T cells in tumor tissue from before therapy (assessed within 14 days before treatment) to after 4 cycles (8 weeks) of therapy to the best clinical response (modified RECIST 1.1 criteria) at the end of Cycle 4 (Week 8) in subjects with previously-treated mesothelioma. (mandatory)

Number and localization (central versus peripheral) of CD8+ cells and Granzyme B+ T cells in tumor tissue obtained by CT-guided biopsies (i.e., image-guided percutaneous lung biopsy) will be determined by IHC by a lab such as Biothera Pharmaceuticals, Inc. (Eagan, MN) and will be correlated with clinical outcome assessed by imaging. Changes in number of CD8+ cells and Granzyme B+ T cells from before therapy (assessed within 14 days before treatment) to after 4 cycles (8 weeks) of therapy will be examined in relation to the best clinical response (modified RECIST 1.1 criteria [35]) at the end of Cycle 4 (Week 8). Other markers such as but not limited to CD4 FoxP3, PD-L1, Pan-cytokeratin, and DAPI. This analysis determined by ELISA assay or comparable technology will be conducted by a lab such as Biothera Pharmaceuticals, Inc. (Eagan, MN). Refer to the CLM for collection, processing, labeling and shipping instructions.

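### Chi-square is named for changes in tissue PD-L1, cytokine expression and CD8+/Granzyme B+ cells, but no cut point is given for any change; analysing the changes as measured would usually keep more power

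*Combined protocol and SAP*

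**What the plan says.** Section 12.6 has five correlative analyses, four of which concern a change during treatment.

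- **Baseline tissue PD-L1.** This is categorical by design: "PD-L1 expression in tumor tissue (categorical based on 5% threshold". It is the only numerical threshold in the section, and it applies to a level before treatment.
- **Change in tissue PD-L1.** Chi-square, with no categories given.
- **Change in cytokine expression.** "Change in cytokine expression in tumor tissue from before therapy" to after four cycles: chi-square, with no categories given.
- **Change in T cells.** "Change in number of CD8+ cells (rich vs. poor) and Granzyme B+ T cells (rich vs. poor) from before therapy" to after four cycles: chi-square. Neither rich nor poor is defined.
- **Change in soluble PD-L1.** Correlation statistics, not chi-square.

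For the four tissue analyses the method is the same sentence: "Chi-square statistics will be computed".

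Elsewhere the same variables are treated as quantities. Section 2.1.3 sets the objective as "Correlate change in number of CD8+, Granzyme B+ T cells in tumor tissue". Section 9.5 speaks of "Changes in number of CD8+ cells and Granzyme B+ T cells from before therapy". Section 9.3 says cytokine expression "will be determined by nanostring or comparable technology".

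**The concern.** Chi-square works on counts in categories. For the changes in PD-L1 and cytokines there are no categories, so someone must choose them. If the choice is made after the data are seen, the p-value loses its meaning. Section 2.1.3 lists 14 genes as examples, so the choice may have to be made many times.

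For the T cells there are labels but no rule. The plan does not say what count makes a sample rich, or how a pair of samples (before and after) becomes one category of change.

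Once a cut is chosen, all differences within a category are ignored. The paired tissue comes from a second CT-guided biopsy in at most 35 subjects, so the information is scarce and costly to the subject. The same section already analyses one biomarker change, soluble PD-L1, without categories.

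**Working it through.** **The plan's own figures.** The documents give no power or sample size for the correlative analyses. The available number of subjects comes from Section 12.3: 33 evaluable, raised to 35.

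- One-sample proportion, 0.20 against 0.40, one-sided 5%, 80% power: [(1.645 × √(0.2 × 0.8) + 0.842 × √(0.4 × 0.6)) / 0.2]² = 28.6. With continuity correction: (28.6/4) × [1 + √(1 + 2/(28.6 × 0.2))]² = 33.4, close to the stated 33.
- 33/0.95 = 34.7, so 35, as stated.

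**Responder numbers.** From the two rates in Section 12.3: 0.40 × 33 = 13.2 (13) and 0.20 × 33 = 6.6 (7); 0.40 × 35 = 14 and 0.20 × 35 = 7.

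**Assumptions not in the documents.** Normally distributed change scores, a 1 SD shift in responders, two-sided 5%, responders compared with all others, complete pairs.

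**Step 1: information kept.** For a normal variable cut so that a proportion p lies below c, the large-sample efficiency relative to the t-test is φ(c)²/[p(1 − p)]. For a median split: 0.3989²/0.25 = 0.64. So 33 subjects carry the information of 33 × 0.637 = 21, and 35 that of 22. A 30/70 cut keeps 58%, and a 20/80 cut 49%.

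**Step 2: power at the actual sizes.** 20,000 simulated trials per setting, chi-square without continuity correction:

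| Subjects / responders | Rank-sum | Chi-square, median split | Chi-square, midpoint cut | True null rejection, median split |
|---|---|---|---|---|
| 33 / 13 | 75% | 46% | 60% | 3.3% |
| 33 / 7 | 57% | 51% | 46% | 8.4% |
| 35 / 14 | 78% | 66% | 63% | 3.9% |
| 35 / 7 | 57% | 52% | 47% | 8.8% |

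The midpoint figure for 33/13 came to 59% in a repeat run, which is within simulation error. Part of the large gap for the median split at 33/13 arises because its true level is only 3.3%. If biopsy pairs are lost and 25 remain (an assumed number), rank-sum against median split is 62% against 38% with 10 responders, and 43% against 26% with 5.

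**Step 3: is chi-square reliable here?** With 33 subjects, 16 lie above the median. With 7 responders the smallest expected count is 7 × 16/33 = 3.4, below the usual 5. The statistic exceeds 3.84 when 0, 1, 6 or 7 responders lie above the median. The exact chance of that under no association is (19,448 + 198,016 + 136,136 + 11,440)/4,272,048 = 8.5%, not 5%. So in the settings where chi-square comes closest to the rank test, its error rate is inflated. With 13 responders the expected count is 13 × 16/33 = 6.3, and this problem does not arise.

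**Step 4: a case where the order reverses.** Assume 33 subjects with 13 responders, a 3 SD jump in 50% of responders and 5% of the others, and a cut fixed beforehand at 2 SD. Chi-square then has about 76% power and the rank test about 56%. The advantage comes from the well-placed cut: under the same model, a median split does worse than the rank test.

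**The case against.** Five points can be made against this.

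- **The gain depends on the effect model.** A uniform shift favours ranks, and Step 4 shows a plausible threshold model that favours a cut. This stands: the documents support neither model. It would justify a cut stated in advance, but none is stated for any change.
- **Rich and poor may describe a transition.** A reader might infer that these labels measure a level at one time and so cannot answer an objective about change. The text does not support that as a firm conclusion, because "Change in number of CD8+ cells (rich vs. poor) and Granzyme B+ T cells (rich vs. poor" can also mean moving from poor to rich, which is a change. What stands is that the terms are undefined and that a transition would ignore any change within a category.
- **Not every biomarker change is affected.** A reader might take the point to cover all of them. It does not: the change in soluble PD-L1 already gets correlation statistics.
- **Two response groups are imposed.** Section 12.6 speaks of best clinical response and treatment outcome, and does not reduce response to two groups. This stands. The 40% share is also the hypothesised overall response rate, not a Week 8 rate. The power figures are therefore illustrations, and the fix must allow for ordered response categories.
- **These analyses are correlative.** They have no stated alpha or power, and nothing in the primary or secondary endpoints rests on them. This stands and limits the severity.

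**Conclusion.** The point holds for three analyses: the changes in tissue PD-L1, in cytokine expression and in CD8+/Granzyme B+ cells. Each is given a categorical test without a rule for making the categories. That gap follows from the text alone and needs no assumption.

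The loss of power is usual, not certain. Under a 1 SD normal shift with 33 to 35 subjects, the rank test is ahead by about 5 to 29 percentage points, depending on the cut and the number of responders. These figures rest on the assumed shift, distribution and two-group response. With about 20% responding, the chi-square approximation is itself unreliable. Severity is minor.

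**What to change.** In Section 12.6, for the three tissue changes:

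- Analyse each change as measured: difference in count or percent for T cells and PD-L1, log2 fold change for genes.
- Relate it to response with a rank-based test. For CR/PR against all others, use the Wilcoxon rank-sum test with a Hodges-Lehmann shift and interval. If response categories are kept, use Kruskal-Wallis or a trend test. State which.
- Keep a contingency test for the baseline PD-L1 5% category, with Fisher's exact test where expected counts are small.
- If a rich/poor table is wanted, fix the cut and the rule for classifying a pair of samples in advance, and show the table descriptively.
- Label the roughly 14 gene analyses as exploratory.

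The cost is wording only, with no extra samples, visits or subjects. The downside is some loss of power if the true effect is a threshold jump that a correctly placed, pre-set cut would have caught.

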13 TRIAL MANAGEMENT

13.1 Data and Safety Monitoring Board (DSMB)

This study will have a Data and Safety Monitoring Board (DSMB). The DSMB is chaired by an independent medical oncologist external to this trial. The DSMB will provide a recommendation to the sponsor-investigator after all information is reviewed. This information will also be provided to HCRN who will distribute to the site investigator/participating sites for submission to their respective IRB, according to the local IRB's policies and procedures.

The DSMB review will include but is not limited to:

- Adverse event summary report
- Audit results, if applicable
- Data related to stopping/decision rules described in study design
- Study accrual patterns
- Protocol deviations

The DSMB will review data a minimum of twice per year during the active study drug administration phase of the study.

13.2 Data Quality Oversight Activities

Remote validation of the EDC system data will be completed on a continual basis throughout the life cycle of the study. Automated edit check listings will be used to generate queries in the EDC system and transmitted to the site to address in a timely fashion. Corrections will be made by the study site personnel.

Monitoring visits to the trial sites may be made periodically during the trial to ensure key aspects of the protocol are followed. For cause visits may occur as necessary. Source documents will be reviewed for verification of agreement with data entered into the EDC system. It is important for the site investigator and their relevant personnel to be available for a sufficient amount of time during the monitoring visits or audit, if applicable. The site investigator and institution guarantee access to source documents by HCRN or its designee.

The trial site may also be subject to quality assurance audit by Eli Lilly, BMS, or their designees as well as inspection by appropriate regulatory agencies.

13.3 Compliance with Trial Registration and Results Posting Requirements

Under the terms of the Food and Drug Administration Modernization Act (FDAMA) and the Food and Drug Administration Amendments Act (FDAAA), the sponsor-investigator of the trial is solely responsible for determining whether the trial and its results are subject to the requirements for submission to the Clinical Trials Data Bank, <http://www.clinicaltrials.gov>. All results of primary and secondary objectives must be posted to CT.gov within a year of completion. The sponsor-investigator has delegated responsibility to HCRN for registering the trial and posting the results on clinicaltrials.gov. Information posted will allow subjects to identify potentially appropriate trials for their disease conditions and pursue participation by calling a central contact number for further information on appropriate trial locations and study site contact information.

14 DATA HANDLING AND RECORD KEEPING

14.1 Data Management

HCRN will serve as the Clinical Research Organization for this trial. Data will be collected through the web-based clinical research platform, a system compliant with Good Clinical Practices and Federal Rules and Regulations. HCRN personnel will coordinate and manage data for quality control assurance and integrity. All data will be collected and entered into the EDC system by study site personnel from participating institutions.

14.2 Case Report Forms and Submission

Generally, clinical data will be electronically captured in the EDC system and correlative results will be captured in the EDC system or other secure database(s). If procedures on the study calendar are performed for standard of care, at minimum, that data will be captured in the source document. Select standard of care data will also be captured in the EDC system, according to study-specific objectives.

The completed dataset is housed at HCRN and is the sole property of the sponsor-investigator's institution. It should not be made available in any form to third parties, except for authorized representatives of appropriate Health/Regulatory Authorities, without written permission from the sponsor-investigator and HCRN. After the initial publication, the complete data set will be available to all HCRN institutions.

14.3 Record Retention

To enable evaluations and/or audits from Health Authorities/HCRN, the investigator agrees to keep records, including the identity of all participating subjects (sufficient information to link records; e.g., hospital records), all original signed informed consent forms, copies of all source documents, and detailed records of drug disposition. To comply with international regulations, the records should be retained by the investigator in compliance with regulations. No records will be destroyed until HCRN confirms destruction is permitted.

14.4 Confidentiality

There is a slight risk of loss of confidentiality of subject information. All records identifying the subject will be kept confidential and, to the extent permitted by the applicable laws and/or regulations, will not be made publicly available. Information collected will be maintained on secure, password protected electronic systems. Paper files that contain personal information will be kept in locked and secure locations only accessible to the study team. Samples that are collected will be identified by a subject study number assigned at the time of registration to the trial.

Subjects will be informed in writing that some organizations, including the sponsor-investigator and his/her research associates, HCRN, Eli Lilly and Company, Bristol-Myers Squibb, IRB, or government agencies, like the FDA, may inspect their medical records to verify the information collected, and that all personal information made available for inspection will be handled in strictest confidence and in accordance with local data protection laws.

If the results of the study are published, the subject's identity will remain confidential.

15 ETHICS

15.1 Institutional Review Board (IRB) Approval

The final study protocol, including the final version of the informed consent form must be approved in writing by an IRB. The investigator must submit written approval to the HCRN office before he or she can enroll any subjects into the study.

The site investigator is responsible for informing the IRB of any amendment to the protocol in accordance with local requirements. In addition, the IRB must approve all advertising used to recruit subjects for the study. The protocol must be re-approved by the IRB annually, as local regulations require.

Progress reports and notifications of serious unexpected adverse drug reactions will be provided to the IRB according to local regulations and guidelines.

15.2 Ethical Conduct of the Study

The study will be performed in accordance with ethical principles originating from the Declaration of Helsinki. Conduct of the study will be in compliance with ICH Good Clinical Practice, and with all applicable federal (including 21 CFR parts 56 & 50), state, or local laws.

15.3 Informed Consent Process

The investigator will ensure the subject is given full and adequate oral and written information about the nature, purpose, possible risks and benefits of the study. Subjects must also be notified they are free to discontinue from the study at any time. The subject should be given the opportunity to ask questions and allowed time to consider the information provided.

The subject's signed and dated informed consent must be obtained before conducting any procedure specifically for the study. The investigator must store the original, signed informed consent form. A copy of the signed informed consent form must be given to the subject.


17 APPENDIX 1: Nivolumab Management Algorithms

These general guidelines constitute guidance to the site Investigator and may be supplemented through discussions with the Sponsor-Investigator by contacting the HCRN project manager. The guidance applies to all immuno-oncology agents and regimens.

As general principle, differential diagnoses should be diligently evaluated according to standard medical practice. Non-inflammatory etiologies should be considered and appropriately treated.

[figure not shown]
Corticosteroids are a primary therapy for immuno-oncology drug-related adverse events. The oral equivalent of the recommended IV doses may be considered for ambulatory patients with low-grade toxicity. The lower bioavailability of oral corticosteroids should be taken into account when switching to the equivalent dose of oral corticosteroids.

Consultation with a medical or surgical specialist, especially prior to an invasive diagnostic or therapeutic procedure, is recommended.

The frequency and severity of the related adverse events covered by these algorithms will depend on the immuno-oncology agent or regimen being used.

GI Adverse Event Management Algorithm

Rule out non-inflammatory causes. If non-inflammatory cause is identified, treat accordingly and continue I-O therapy. Opiates/narcotics may mask symptoms of perforation. Infliximab should not be used in cases of perforation or sepsis.

[figure not shown]

Patients on IV steroids may be switched to an equivalent dose of oral corticosteroids (e.g. prednisone) at start of tapering or earlier, once sustained clinical improvement is observed. Lower bioavailability of oral corticosteroids should be taken into account when switching to the equivalent dose of oral corticosteroids.

Updated 05-Jul-2016

Renal Adverse Event Management Algorithm

Rule out non-inflammatory causes. If non-inflammatory cause, treat accordingly and continue I-O therapy

[figure not shown]

Patients on IV steroids may be switched to an equivalent dose of oral corticosteroids (e.g. prednisone) at start of tapering or earlier, once sustained clinical improvement is observed. Lower bioavailability of oral corticosteroids should be taken into account when switching to the equivalent dose of oral corticosteroids.

Updated 05-Jul-2016

Pulmonary Adverse Event Management Algorithm

Rule out non-inflammatory causes. If non-inflammatory cause, treat accordingly and continue I-O therapy. Evaluate with imaging and pulmonary consultation.

[figure not shown]

Patients on IV steroids may be switched to an equivalent dose of oral corticosteroids (e.g. prednisone) at start of tapering or earlier, once sustained clinical improvement is observed. Lower bioavailability of oral corticosteroids should be taken into account when switching to the equivalent dose of oral corticosteroids.

Updated 05-Jul-2016

Hepatic Adverse Event Management Algorithm

Rule out non-inflammatory causes. If non-inflammatory cause, treat accordingly and continue I-O therapy. Consider imaging for obstruction.

Patients on IV steroids may be switched to an equivalent dose of oral corticosteroids (e.g. prednisone) at start of tapering or earlier, once sustained clinical improvement is observed. Lower bioavailability of oral corticosteroids should be taken into account when switching to the equivalent dose of oral corticosteroids.

[figure not shown]
*I-O therapy may be delayed rather than discontinued if AST/ALT \leq 8 x ULN or T.bili \leq 5 x ULN.

**The recommended starting dose for grade 4 hepatitis is 2 mg/kg/day methylprednisolone IV.

Updated 05-Jul-2016

Endocrinopathy Management Algorithm

Rule out non-inflammatory causes. If non-inflammatory cause, treat accordingly and continue I-O therapy. Consider visual field testing, endocrinology consultation, and imaging.

[figure not shown]

Patients on IV steroids may be switched to an equivalent dose of oral corticosteroids (e.g. prednisone) at start of tapering or earlier, once sustained clinical improvement is observed. Lower bioavailability of oral corticosteroids should be taken into account when switching to the equivalent dose of oral corticosteroids.

Updated 05-Jul-2016

Skin Adverse Event Management Algorithm

Rule out non-inflammatory causes. If non-inflammatory cause, treat accordingly and continue I-O therapy.

Patients on IV steroids may be switched to an equivalent dose of oral corticosteroids (e.g. prednisone) at start of tapering or earlier, once sustained clinical improvement is observed. Lower bioavailability of oral corticosteroids should be taken into account when switching to the equivalent dose of oral corticosteroids.

[figure not shown]
*Refer to NCI CTCAE v4 for term-specific grading criteria.

^If SJS/TEN is suspected, withhold I-O therapy and refer patient for specialized care for assessment and treatment. If SJS or TEN is diagnosed, permanently discontinue I-O therapy.

Updated 05-Jul-2016

Neurological Adverse Event Management Algorithm

[figure not shown]
Rule out non-inflammatory causes. If non-inflammatory cause, treat accordingly and continue I-O therapy.

Patients on IV steroids may be switched to an equivalent dose of oral corticosteroids (e.g. prednisone) at start of tapering or earlier, once sustained clinical improvement is observed. Lower bioavailability of oral corticosteroids should be taken into account when switching to the equivalent dose of oral corticosteroids.

Updated 05-Jul-2016

Myocarditis Adverse Event Management Algorithm

Patients on IV steroids may be switched to an equivalent dose of oral corticosteroids (eg, prednisone) at start of tapering or earlier, once sustained clinical improvement is observed. Lower bioavailability of oral corticosteroids should be taken into account when switching to the equivalent dose of oral corticosteroids.

Prophylactic antibiotics should be considered in the setting of ongoing immunosuppression.

ATG = anti-thymocyte globulin; BNP = B-type natriuretic peptide; ECG = electrocardiogram; IV = intravenous; MRI = magnetic resonance imaging

320

Approved v19.0 930038243 20.0
